APPENDIX 6: Radiotherapy Guidance for Symptomatic Lesions

- Palliative radiotherapy to control symptoms (including gamma knife technique), eg to control brain disease, is permitted.
- For brain and thoracic radiotherapy (only to control symptoms), a 7- to 10-day study drug washout period before the procedure and 1 week period after the procedure before restarting study drug(s) is advised.
- All radiotherapy related toxicities should be managed and ideally resolved before restarting study drug(s).
- Investigators should consider the radiotherapy when assessing causality if there are any localized AEs following the procedure.
- If any lesions (including brain or thoracic disease) are **asymptomatic**, then radiation would not be permitted.

a Non-CR/non-PD is preferred over stable disease for nontarget disease since stable disease is increasingly used as endpoint for assessment of efficacy in some studies, so to assign this category when no lesions can be measured is not advised.

CBR	clinical benefit rate
cfDNA	cell-free DNA
CI	confidence interval
CR	complete response
CSR	clinical study report
CT	computed tomography
CTCAE	Common Terminology Criteria for Adverse Events
DLT	dose-limiting toxicity
ECG	electrocardiogram
ECOG	Eastern Cooperative Oncology Group
eCRF	electronic case report form
FAS	full analysis set
HR	hazard ratio
IDMC	independent data monitoring committee
IMP	investigational medicinal product
MedDRA	Medical Dictionary for Regulatory Activities
MRI	magnetic resonance imaging
MUGA	multigated acquisition
NCI	National Cancer Institute
NE	not evaluable
NSCLC	non-small cell lung cancer
NTL	nontarget lesion
OR	objective response
ORR	objective response rate
OS	overall survival
PD	progressive disease
PFS	progression-free survival

G1 Therapeutics, Inc.
Clinical Study Protocol G1T38-03
Statistical Analysis Plan

Abbreviation	Term
PK	pharmacokinetic(s) or PK analysis set, per context
PP	per protocol
PR	partial response
PT	preferred term
QTcF	QT interval corrected by Fridericia's formula
RECIST	Response Evaluation Criteria in Solid Tumors
RES	response evaluable analysis set
RP2D	recommended Phase 2 dose
SAE	serious adverse event
SAP	statistical analysis plan
SD	stable disease
SMC	safety monitoring committee
SOC	system organ class
StD	standard deviation
TEAE	treatment-emergent adverse event
TL	target lesion
WHO	World Health Organization
WHODrug	World Health Organization Drug Dictionary

1. INTRODUCTION

The purpose of this statistical analysis plan (SAP) is to describe the detailed analysis and reporting, including tables, listings, and figures, for G1T38-03 (“38-03”), the study of G1T38 in combination with Osimertinib in patients with EGFR mutation-positive metastatic non-small cell lung cancer (NSCLC). The analyses specified in this SAP will be used to support the clinical study report (CSR).

Study measurements and assessments, planned statistical methods, and derived variables are summarized in this plan. Planned tables, figures, and listings to accompany this SAP are specified in a Tables, Figures, and Listings (TLF) shells. All decisions regarding final analyses, as defined in this SAP document, have been made prior to locking the database. Any significant change from the planned analysis in this SAP to provide results for inclusion in the CSR, will be clearly documented in the CSR.

This version of the SAP is based on the protocol version 4.0 dated 02 September 2019. Although the protocol includes study Part 1 and Part 2, Part 2 will not be conducted due to a corporate strategy shift. This SAP describes the analyses of the data collected from Part 1 only.

2. STUDY DESIGN OVERVIEW (PART 1)

This section provides high level information of the study design. Unless as documented in [Section 7](#) (Change From the Protocol), any discrepancies between the protocol language and the text in this section are inadvertent and should not be interpreted as a change to the protocol design.

2.1. Study Objectives

Primary Objective

The primary objectives of Part 1 (Phase 1b) of the study are to:

- Evaluate dose-limiting toxicities (DLTs) associated with G1T38 administered with osimertinib
- Determine the recommended Phase 2 dose (RP2D) of G1T38 administered with osimertinib
- Evaluate the safety and tolerability of G1T38 administered with osimertinib

Secondary Objectives

The secondary objectives of the study are to:

- Assess PFS using investigator assessments (RECIST v1.1)
- Assess response rate and disease control rate (DCR) based on RECIST v1.1 (investigator assessed)
- Assess overall survival (OS)

G1 Therapeutics, Inc.
Clinical Study Protocol G1T38-03
Statistical Analysis Plan

- Assess 1-year PFS (investigator assessed)
- Assess the effect of osimertinib on pharmacokinetic (PK) parameters of G1T38

Refer to protocol Section 5 for other study objectives and endpoints.

2.2. Study Design

Study 38-03 is an open-label study evaluating the effect of osimertinib on the PK parameters of G1T38 and the safety and tolerability of escalating doses of G1T38 in combination with osimertinib to determine the RP2D. The study includes 3 phases: Screening Phase, Treatment Phase, and Survival Follow-up Phase. The Treatment Phase begins on the day of the first dose of study drug and completes at the Post-Treatment Visit.

Six patients will be enrolled in the first cohort to assess the potential effect of osimertinib on the PK parameters of G1T38. Projected dose levels are presented in Table 6-1 of the Protocol. Patients will receive a single oral dose of G1T38 200 mg on Cycle 1 Day -16 and blood samples for G1T38 PK evaluation will be collected over the subsequent 48-hour period. Patients will then receive oral osimertinib 80 mg once daily without G1T38 on Cycle 1 Days -14 to -3, and then both G1T38 and osimertinib on Cycle 1 Day -2, after which blood samples for G1T38 PK evaluation will be collected over the subsequent 48-hour period. Osimertinib once-daily dosing will continue on Cycle 1 Day -1 and through the end of the Treatment Phase. On Cycle 1 Day 1, patients will begin G1T38 once-daily dosing, which will continue through the end of the Treatment Phase (note: there is no Day 0 in the study). DLTs will be evaluated from Cycle 1 Day -16 through Cycle 1 Day 28 (the DLT period). A safety monitoring committee (SMC) will evaluate all safety and available PK data through the DLT period for Cohort 1 prior to the enrollment of additional cohorts.

Thereafter, additional sequential dose-escalation cohorts may be enrolled using a standard 3 + 3 design and will follow the same schedule as described for the first cohort.

All dose escalation/de-escalation recommendations made by the SMC will be based on review of safety and available PK from the DLT period of the current cohort, as well as the cumulative safety data from all patients enrolled. Further details with respect to decision making will be described in the SMC Charter.

Patients will be observed for a DLT during the first cycle of treatment (Cycle 1 Day -16 through Cycle 1 Day 28). Please refer to protocol sections 6.1.1.1. for more information regarding the dose escalation plan as it relates to DLT findings.

2.3. Number of Patients

For Part 1, six patients will be enrolled in the first cohort and additional cohorts may be enrolled using a standard 3 + 3 design with a maximum of 36 patients. The actual number of patients will depend on the number of dose levels/cohorts that are tested.

3. ANALYSIS POPULATIONS (PART 1)

3.1 Definition of Analysis Populations

3.1.1. All Screened Patients

The all screened patients set includes all subjects who consented to participate in the study and completed any screening assessments.

3.1.2. All Enrolled Patients

Enrolled patients are those who consented to participate in the study and have met entry criteria.

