The safety analysis will include all treated patients. Descriptive statistics of safety will be presented. All treatment-emergent AEs, drug-related AEs, serious adverse events (SAEs), and drug-related SAEs will be tabulated using worst grade per National Cancer Institute (NCI) CTCAE, Version 4.03 criteria by system organ class and preferred term. On-study laboratory parameters including hematology, chemistry, and liver function tests will also be summarized using worst grade per NCI CTCAE, Version 4.03 criteria.

Rationale for Number of Patients

It is estimated that up to 36 patients will be enrolled in the dose-escalation part of the study (Part 1). The actual number of patients will depend on the number of dose levels/cohorts that are tested.

For the randomized part of the study (Part 2), it is assumed that the overall 1-sided type I error rate is 0.1 and the type II error rate used to compute sample size is 0.20 (corresponding to 80% power). Patients will be randomized using a 1:1 treatment allocation ratio between the 2 treatment groups (osimertinib versus G1T38 + osimertinib).

Assuming a 10.1 month median PFS for the osimertinib group based on historical data, and an HR of 0.6, the required number of PFS events is 70. Assuming an accrual period of 12 months and an additional follow-up period of 18 months after the last patient is enrolled, the calculated total sample size is 98 patients. Allowing for a dropout/lost-to-follow-up rate of approximately 10%, gives an adjusted total sample size of 108 patients for Part 2.

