3.1.3. Safety Population

The safety population will include all enrolled patients who were administered at least 1 dose of study drug (G1T38 or osimertinib). All safety analyses will be assessed using the safety population. Analyses using the safety population will be conducted on the basis of the actual treatment received.

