3.1.4. Response Evaluable Analysis Set (RES)

The response evaluable analysis set (RES) will include all patients who are in the safety population and who have at least one measurable tumor lesion (target lesion(s)) at the baseline tumor assessment, and either (i) have at least one post-baseline tumor assessment, or (ii) do not have post-baseline tumor assessment but have clinical progression as noted by the investigator, or (iii) have died due to disease progression before their first post-baseline tumor scan. The RES will be used for analyses of tumor response.

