3.1.5. Full Analysis Set (FAS)

The Full Analysis Set (FAS) will include all enrolled patients who were administered at least one dose of continuous daily of G1T38 (i.e., Cycle 1 Day 1). All analyses using FAS will be conducted by the dose level cohort that was assigned at enrollment. The FAS is the primary analysis set for efficacy analyses, unless otherwise specified.

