Safety assessments (other than AEs) during treatment period is defined as assessment that is evaluated between the date of first dose of study drug and the date of last dose of study drug + 29 days. Assessments occur on or after last dose of study drug + 30 days will be counted as assessments during post-treatment period. If start date of survival follow up is available, assessments during post-treatment period should occur prior to the start of survival. If the last dose date of study drug is missing, any assessment/event occurring after the start of study drug will be considered as during treatment period.

All data will be listed for all enrolled patients.

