5.2.2. Protocol Deviations

Protocol deviations will be classified as major or minor for severity based on if they may affect the ability to assess the safety and efficacy of study drug. The classification of protocol deviations will be finalized at the Classification Meeting prior to database lock.

The number and percentage of patients by dose level and overall and deviation type will be presented for all major protocol deviations for safety population. All protocol deviations will be listed including detailed description, deviation type and subtype and classification for major or minor based on data recorded on Protocol Deviation Logs, including unavoidable protocol deviations due to COVID-19 illness and/or COVID-19 control measures, provided by PAREXEL Medical.

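### Read literally, the SAP's definition of an enrolled patient would leave a dosed patient with an entry-criterion breach out of the CSR safety tables

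*SAP*

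**What the plan says.** The SAP text that matters:

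- Section 3.1.2: "Enrolled patients are those who consented to participate in the study and have met entry criteria".
- Section 3.1.3: "The safety population will include all enrolled patients who were administered at least 1 dose of study drug (G1T38 or osimertinib"; and then "All safety analyses will be assessed using the safety population".
- Section 3.1.4: "The response evaluable analysis set (RES) will include all patients who are in the safety population", with further conditions on measurable disease and follow-up.
- Section 3.1.5: the FAS "will include all enrolled patients who were administered at least one dose of continuous daily of G1T38".
- Section 5.1.1: "All data will be listed for all enrolled patients".
- Section 5.2.2: "The number and percentage of patients by dose level and overall and deviation type will be presented for all major protocol deviations for safety population".
- Section 5.2.1: the disposition list gives treated patients and the safety population as the same category.

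The protocol synopsis puts no eligibility condition on the safety analysis: "The safety analysis will include all treated patients". Protocol 12.2.1 does start from enrolled patients with at least one dose, but the protocol does not define enrolled by having met the criteria. It treats enrollment as an event. Eligibility is settled beforehand (Section 9.1), enrollment is marked at Cycle 1 Day -16 in Table 9-1, and the IWRS assigns the cohort (Section 8.2). SAP Section 7, which lists departures from the protocol, has no entry on the definition of enrolled or of the safety population.

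**The concern.** SAP 3.1.2 makes meeting the criteria part of what enrolled means, and the other sets inherit that condition. Some exclusions depend on medication history and can come to light after dosing: strong BCRP or CYP3A4 inhibitors within 14 days, or gastric pH agents within 7 days (Protocol 7.1.2, items 5, 7 and 8). The BCRP exclusion bears directly on G1T38 exposure (Protocol 8.5.3). A programmer who applies 3.1.2 as written would drop such a patient from the adverse event, laboratory, ECG and vital signs tables, although the patient received study drug.

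Safety and tolerability and DLTs are primary objectives of Part 1. Cohorts have 3 to 6 patients and the maximum is 36, so one lost patient changes what is reported. The major-deviation table would also lose its most important kind of entry, a patient dosed in breach of eligibility.

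**Working it through.** No sample size, power or error rate depends on this point, so there is no planned figure to reproduce. The check traces the set definitions and then illustrates the size.

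**1. The sets.** Let M be patients who met the entry criteria and D patients with at least one dose; all are taken to have consented.

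- Enrolled (SAP 3.1.2) = M.
- Safety population (SAP 3.1.3) = M and D.
- RES (SAP 3.1.4) = a subset of M and D.
- FAS (SAP 3.1.5) = M and at least one continuous daily dose of G1T38.
- General listings (SAP 5.1.1) = M.
- Safety analysis (protocol synopsis) = D.

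The synopsis set minus the SAP safety population is D and not M: exactly the patients who were dosed without meeting a criterion.

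**2. The deviation table.** Its population is M and D. The patients in it with an entry-criterion breach are (M and D) and not M, which is empty. Under the literal definition the count of such breaches among dosed patients is zero by construction.

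**3. Size within one cohort.** Take a six-patient cohort in which one dosed patient with a DLT turns out to have breached a criterion. Removing that patient takes one from both numerator and denominator. Intervals are exact 95% Clopper-Pearson.

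| DLTs in cohort | All dosed patients | SAP 3.1.2 read literally |
|---|---|---|
| 1 | 1/6 = 16.7% (0.4% to 64.1%) | 0/5 = 0% (0% to 52.2%) |
| 2 | 2/6 = 33.3% (4.3% to 77.7%) | 1/5 = 20.0% (0.5% to 71.6%) |

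In the second row, two DLTs in six is the count at which Protocol 6.1.1.1 takes the MTD as exceeded for Cohort 1. A table showing 1/5 would not match the count that the safety monitoring committee (SMC) had acted on.

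**4. How likely is at least one such patient?** The documents give no breach rate, so q is an assumption. The chance is 1 − (1 − q)^n.

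| Assumed q | n = 6 | n = 36 | Expected number in 36 (36 × q) |
|---|---|---|---|
| 2% | 11% | 52% | 0.7 |
| 5% | 26% | 84% | 1.8 |
| 10% | 47% | 98% | 3.6 |

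**The case against.** The strongest reply is that the definition is procedural. Protocol 9.1 has eligibility determined before enrollment, and Protocol 7.1.1 has it reviewed and documented before inclusion. Having met the criteria may therefore mean only that the patient passed that check, as opposed to being a screen failure. Nothing in the SAP says that a patient loses enrolled status when a breach is found later. The disposition list in SAP 5.2.1 equates treated patients with the safety population, and a deviation table run on that population makes most sense if patients with breaches stay in it. SAP 3.1.3 also follows Protocol 12.2.1 closely, so the phrase about enrolled patients was carried over; only 3.1.2 adds the eligibility condition. All of this stands as evidence of intent. It does not settle the wording, because 3.1.2 fixes no time at which the criteria are judged, and two programmers could produce different denominators.

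A reader might go further and infer that the breach disappears from the report altogether. The documents do not support that. SAP 5.2.2 lists all protocol deviations from the deviation logs, SAP 5.2.10 lists all AEs, and a separate listing covers patients who met Hy's law. None of these sentences is limited to enrolled patients, although the general rule in 5.1.1 is.

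Nor do the documents support an effect on dose escalation or the RP2D. Those decisions rest on SMC review under Protocol 6.1.1 and 12.2.2.1, not on the SAP's populations.

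A QTc above 470 msec found after dosing is a tempting example but a poor one. Exclusion 13a is judged on the screening clinic machine's value, so a later or central reading does not breach it.

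**Conclusion.** The point holds as a wording defect with a real consequence if followed. As written, SAP 3.1.2 to 3.1.5 take a dosed patient with an entry-criterion breach out of the CSR safety tables and make the major-deviation table unable to count that patient. This conflicts with the protocol synopsis and with the SAP's own disposition list, and Section 7 does not record it. Exclusion was probably not intended, but the safety denominator in a study whose primary objectives are safety objectives should not turn on interpretation.

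The size is one patient at a time: 1/6 against 0/5, or 2/6 against 1/5. The DLT proportion stands in for any safety proportion here, because SAP 5.2.10 names no DLT table and Protocol 12.3 says only that DLTs will be summarized or listed. A comparison of 1/3 with 0/2 would mislead, since one DLT among three triggers three more patients under Protocol 6.1.1.1.

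Two things remain unknown: how often such breaches occur, and which way their removal would move toxicity rates. A reader might infer that rates would be biased downward, but a breach of timing or paperwork need not carry added risk, and the documents give no basis for a direction.

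**What to change.** 1. In SAP 3.1.2, define enrolled patients by the event: consented and assigned to a Part 1 cohort through enrollment in the IWRS, regardless of any eligibility breach found later.
2. In SAP 3.1.3, define the safety population as all patients who received at least one dose of G1T38 or osimertinib, regardless of eligibility. This agrees with the protocol synopsis.
3. Let the FAS, RES, general listings and deviation table inherit these definitions, so that entry-criterion breaches in dosed patients are counted as deviations and not removed from the denominator.

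A line in SAP Section 7 stating this reading would help, because Protocol 12.2.1 keeps the word enrolled without defining it. The cost is two sentences of SAP text plus that note. No new data are needed and no planned sample size changes.

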3.1.3. Safety Population

The safety population will include all enrolled patients who were administered at least 1 dose of study drug (G1T38 or osimertinib). All safety analyses will be assessed using the safety population. Analyses using the safety population will be conducted on the basis of the actual treatment received.

3.1.4. Response Evaluable Analysis Set (RES)

The response evaluable analysis set (RES) will include all patients who are in the safety population and who have at least one measurable tumor lesion (target lesion(s)) at the baseline tumor assessment, and either (i) have at least one post-baseline tumor assessment, or (ii) do not have post-baseline tumor assessment but have clinical progression as noted by the investigator, or (iii) have died due to disease progression before their first post-baseline tumor scan. The RES will be used for analyses of tumor response.

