7.1.1. Inclusion Criteria

Patient eligibility shall be reviewed and documented by an appropriately qualified member of the investigator's study team before patients are included in the study. Patients must meet all of the following inclusion criteria to be eligible for enrollment into the study:

- 1. Provision of signed and dated written informed consent prior to any study specific procedures, sampling, and analysis
- 2. Women or men, 18 years or older
- 3. Histologic or cytologic confirmed diagnosis of NSCLC
- 4. Stage IV NSCLC
- 5. Documented EGFR mutation (at any time since the initial diagnosis of NSCLC) known to be associated with EGFR TKI sensitivity (including G719X, exon 19 deletion, L858R, L861Q). Patients in Part 1 that are EGFR TKI treatment naive will be enrolled based on a locally available EGFR mutation test result that has been FDA-approved and performed in a Clinical Laboratory Improvement Amendments (CLIA)-certified laboratory (US sites) or based on a locally available EGFR mutation test result that has been performed in an accredited laboratory (sites outside of the US).
 - a. *Part 2 Only*: Tumor EGFR T790M mutation-positive status after documented disease progression on first-line treatment with a first or second generation EGFR TKI. Patients will be enrolled based on a locally available T790M mutation test result (tumor biopsy or cell-free DNA [cfDNA]) that has been FDA-approved (eg, cobas[®] EGFR Mutation Test v2, FoundationOne CDxTM) and performed in a CLIA-certified laboratory (US sites) or a locally available T790M mutation test result (tumor biopsy or cfDNA) that has been performed in an accredited laboratory (sites outside of the US). Testing for the presence of the T790M mutation in plasma specimens (cfDNA) is recommended only in patients for whom a tumor biopsy cannot be obtained.
- 6. Eastern Cooperative Oncology Group (ECOG) performance status of 0 or 1, with no deterioration over the previous 2 weeks and a minimum life expectancy of 12 weeks

- 7. Evaluable disease (Part 1 only) or measurable disease as defined in Response Evaluation Criteria in Solid Tumors (RECIST), Version 1.1, as determined by the investigator

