5.2.9. Efficacy Analyses

5.2.9.1 Analysis of Tumor Response

The number and percentage of subjects in each category of BOR according to programmatically-derived tumor response (CR, PR, SD, PD, or NE) based on investigator's measurements will be presented by dose level and overall. Also, the number and percentage of subjects in each category of BOR (Confirmed CR, Confirmed PR, SD, PD, or NE) based on CRF collected timepoint response (confirmed) will be summarized by dose level and overall. Similar analyses will be repeated for ORR and DCR.

Estimates of response rate, along with its associated exact 95% two-sided CIs using Clopper-Pearson method will be computed for ORR, BOR, and DCR within each treatment group.

The above analyses will be based on the RES. Analysis will be repeated for FAS based on programmatically derived BOR (confirmed) and DCR with additional category of Non-CR/Non-PR.

In addition to confirmed response (CR_{confirmed}, PR_{confirmed} and ORR_{confirmed}) in BOR summary, both confirmed response and unconfirmed response (CR_{unconfirmed}, PR_{unconfirmed}, and ORR_{unconfirmed}) will be presented in a separated BOR summary based on programmatically derived response for response evaluable population.

Detailed tumor assessment data from CRF will be listed together with derived response for target lesion(s) and derived time point response for all enrolled patients.

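### The response evaluable set drops never-scanned patients unless they progressed, so any such exclusion can only raise the reported Part 1 ORR and DCR

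*SAP*

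**What the plan says.** SAP 3.1.4 starts from the safety population (any dose of either drug) and requires at least one target lesion at baseline. A patient with any post-baseline tumor assessment then qualifies. A patient without one qualifies only if they "do not have post-baseline tumor assessment but have clinical progression as noted by the investigator, or (iii) have died due to disease progression" before a first scan. The section adds: "The RES will be used for analyses of tumor response".

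SAP 3.1.5 states: "The FAS is the primary analysis set for efficacy analyses, unless otherwise specified". Tumor response is otherwise specified. After describing the BOR, ORR and DCR summaries by dose level, SAP 5.2.9.1 says: "The above analyses will be based on the RES". A second analysis follows: "Analysis will be repeated for FAS based on programmatically derived BOR (confirmed) and DCR with additional category of Non-CR/Non-PR". The separate summary that includes unconfirmed responses is planned for the response evaluable population only.

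Three other provisions bear on the point:

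- Protocol 7.1.1, criterion 7, admits "Evaluable disease (Part 1 only) or measurable disease", so Part 1 may contain patients with no target lesion.
- SAP 4.1.2.1 scores anyone in the analysis set without a confirmed CR or PR as a non-responder. It places the first scheduled scan at study day 56, with a window of day 49 to 63.
- Protocol 9.4, 10.1 and 11.3 provide for tumor assessment after study drug is stopped without progression.

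**The concern.** Membership of the RES depends on what happened to the patient after treatment began. Take two patients with target lesions and no post-baseline scan. If one dies of progression, that patient stays in the denominator as a failure. If the other dies of toxicity, that patient disappears. The split also rests on the assigned cause of death and on the investigator's judgement of clinical progression, in an open-label study.

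The rule also conflicts with the SAP's own handling of inadequate data. Under the text below SAP Table 4, a patient whose only scan shows stable disease before day 49 gets a BOR of NE. That patient stays in the RES as a non-responder. The same patient without that scan, and without progression, is removed.

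A patient who is never scanned cannot have a response or documented disease control, so the error has one direction: each removal raises ORR and DCR. Response is to be shown by dose level, and with cohorts of three to six one removed patient visibly changes a rate. At stake is whether the ORR and DCR in the study report describe the treated patients with measurable disease, or only those who were scanned or progressed.

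**Working it through.** The plan states no figure to reproduce. Part 1 is descriptive (SAP 5.1.1), its 36 patients are a maximum (SAP 2.3), and no count of unscanned patients is given. What follows is an illustration on stated assumptions.

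**Notation.** n = safety-population patients with a baseline target lesion; r = responders; k = those among the n with no post-baseline assessment, no clinical progression and no progression death.

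**Formula.** ORR in all n is r/n. ORR in the RES is r/(n-k). The ratio is n/(n-k), which is 1 when k = 0 and exceeds 1 otherwise. DCR has the same ratio, because the k patients contribute nothing to its numerator either.

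**All cohorts together.** Assume n = 36 (the cap, all measurable) and r = 25. This is close to the 70% historical rate for osimertinib alone in Protocol 4.1, used only as a plausible level.

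| k | RES ORR | Rise over 25/36 = 69.4% |
|---|---|---|
| 1 | 25/35 = 71.4% | 2.0 points |
| 2 | 25/34 = 73.5% | 4.1 points |
| 3 | 25/33 = 75.8% | 6.3 points |

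The exact 95% interval for 25/36 is 51.9% to 83.7%, about 32 points wide.

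**One dose cohort.** Assumed counts:

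| n | r | r/n | k = 1 | k = 2 |
|---|---|---|---|---|
| 6 | 3 | 50.0% | 3/5 = 60.0% | 3/4 = 75.0% |
| 6 | 4 | 66.7% | 4/5 = 80.0% | 4/4 = 100% |
| 3 | 2 | 66.7% | 2/2 = 100% | not applicable |

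**Does the FAS repeat recover r/n?** Assume 36 patients, all in the FAS: 6 without target lesions and without a CR, 30 with target lesions, 21 responders and k = 2.

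- RES: 21/28 = 75.0%
- All with target lesions: 21/30 = 70.0%
- FAS: 21/36 = 58.3%

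The RES and FAS differ by 16.7 points. Of these, 5.0 come from the exclusion rule and 11.7 from adding patients without target lesions, for whom SAP Table 3-2 has no PR category. For DCR the FAS can move either way, because SAP 4.1.2.1 counts Non-CR/Non-PD as disease control in such patients.

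**Coverage of the FAS repeat.** It is limited to derived, confirmed BOR and DCR. ORR must be read off the BOR table, and the CRF-based and unconfirmed summaries are not repeated. The FAS also requires the start of continuous G1T38 on Cycle 1 Day 1. A patient lost between Day -16 and Day -1 with no scan and no progression is therefore in neither set.

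**The case against.** **Stopping early does not remove a patient.** A reader might infer that anyone who stops drug before the first scheduled scan is lost. The documents do not support that. Scans continue every 8 weeks after a stop without progression (Protocol 9.4, 10.1). If no later scans are planned and none was done in the prior 4 weeks, one is called for at the Discontinuation visit (10.1) or the Post-Treatment Visit (11.3). Any post-baseline assessment suffices for the RES, with no minimum day. This stands: only patients who never get a scan are affected, chiefly through death, withdrawal or loss to follow-up.

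**The effect on dose choice is not shown.** A reader might also infer that inflation is greatest at the most toxic dose and could steer the recommended Phase 2 dose. Protocol 6.1.1 does list efficacy among the things Part 1 assesses. It also replaces patients who leave the DLT period for non-toxicity reasons only, so a link with toxicity is plausible. But no exclusion counts by dose exist. Protocol 12.2.2.1 rests the dose decision on safety and PK data. The SAP analysis runs only after all Part 1 patients have discontinued (SAP 6), and Part 2 will not open (SAP 1).

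**The FAS already covers it.** The FAS needs no scan, counts these patients as non-responders and gives a lower ORR. RES and FAS may therefore bracket the rate wanted, as they do in the example above. Set sizes are tabulated (SAP 5.2.1), and tumor data are listed for all enrolled patients. This is partial mitigation. The bracket was 16.7 points wide, mostly for an unrelated reason, and readers should not have to rebuild the rate from listings.

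**The rule follows the protocol.** Protocol 12.2.1 has the same asymmetry and confined the FAS to Part 2, so the Part 1 repeat is an addition. That explains the choice but does not remove the bias.

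**Conclusion.** The concern holds in a limited form. The RES entry rule depends on outcome, and its bias can only favour the drug combination: ORR and DCR are multiplied by n/(n-k). No planned analysis gives the response rate in all treated patients with measurable disease.

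On the assumed inputs the effect is modest overall, at 2.0 to 6.3 points for one to three exclusions in 36, well inside the sampling uncertainty. It is large within a cohort of six, at 10 to 25 points for one or two exclusions when three respond. It is zero if every patient with a target lesion is scanned or progresses first. The values of n, r and k are assumptions; the direction is not.

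The consequence is confined to how Part 1 ORR and DCR are reported. The documents do not show that rates are in fact inflated, that inflation is worst at the highest dose, or that dose selection is affected.

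**What to change.** In SAP 3.1.4 and 5.2.9.1, base BOR, ORR and DCR on all safety-population patients with at least one baseline target lesion. Do not require the start of continuous G1T38. That condition would newly drop lead-in patients, including some who progress and whom the present RES keeps.

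Score a patient with no post-baseline assessment, for any reason other than progression, as BOR NE, non-responder and without disease control. Apply the same denominator to the derived, CRF-based and unconfirmed summaries.

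Keep the present RES as a sensitivity analysis. List every patient it excludes, with the reason, by dose level, so that k is visible. Record the departure from Protocol 12.2.1 in SAP Section 7, before database lock.

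The cost is SAP wording, one repeated table and one short listing, with no new data. The headline ORR and DCR may become slightly less favourable.
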